6.3.3 Variables

The following variables will be collected for each AE;

- AE diagnosis/description
- The date and time when the AE started and stopped
- Intensity grading according to revised National Cancer Institute CTCAE version 4.03
- Whether the AE is serious or not
- Investigator causality rating against the IP (yes or no)
- Action taken with regard to IP
- AE caused patients' withdrawal from study (yes or no)
- Outcome

In addition, the following variables will be collected for SAEs:

- Date AE met criteria for SAE
- Date Investigator became aware of SAE
- AE is serious due to
- Date of hospitalisation
- Date of discharge
- Probable cause of death
- Date of death
- Autopsy performed
- Causality assessment in relation to study procedure(s)
- Causality assessment to other medication
- Description of AE.

It is important to distinguish between serious and severe AEs. Severity is a measure of intensity whereas seriousness is defined by the criteria in Section 6.2. An AE of severe intensity need not necessarily be considered serious. For example, nausea that persists for several hours may be considered severe nausea, but not a SAE unless it meets the criteria shown in Section 6.2. On the other hand, a stroke that results in only a limited degree of disability may be considered a mild stroke but would be a SAE when it satisfies the criteria shown in Section 6.2.

The grading scales found in the revised National Cancer Institute CTCAE version 4.03 will be utilised for all events with an assigned CTCAE grading. For those events without assigned CTCAE grades, the recommendation in the CTCAE criteria that converts mild, moderate and severe events into CTCAE grades should be used. A copy of the CTCAE version 4.03 can be downloaded from the Cancer Therapy Evaluation Program website (<http://ctep.cancer.gov>).

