2.3 Safety objectives

Safety Objective:	Outcome Measure:
To examine the safety and tolerability [¹¹ C]osimertinib IV doses and multiple oral doses of osimertinib in NSCLC patients with BM.	Assessment of AEs graded by the Common Terminology Criteria for Adverse Events (CTCAE) version 4.03, standard 12-lead ECGs, physical examination, vital signs (including blood pressure [BP], pulse), and evaluation of laboratory parameters (clinical chemistry, haematology, and urine analysis).

AE: Adverse event; BM: Brain metastases; IV: Intravenous; NSCLC: Non-small cell lung cancer.

CCI

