6.3.4 Causality collection

The Investigator will assess causal relationship between the IP and each AE, and answer 'yes' or 'no' to the question 'Do you consider that there is a reasonable possibility that the event may have been caused by the IP?'

For SAEs causal relationship will also be assessed for other medication and study procedures. Note that for SAEs that could be associated with any study procedure the causal relationship is implied as 'yes'.

A guide to the interpretation of the causality question is found in Appendix A to the CSP.

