7.1.1 Osimertinib

Osimertinib 40 mg and 80 mg film-coated oral tablets, manufactured by AstraZeneca will be provided for the study. Osimertinib 40 mg film-coated tablets will only be provided if dose reduction is required.

At each dispensing visit, sufficient osimertinib for each study period, plus overage, will be dispensed. Individual bottles will be dispensed in accordance with local practice.

Osimertinib tablets will be packed in high-density polyethylene (HDPE) bottles with child resistant closures. Bottles will be dispensed to patients in the AstraZeneca packing provided. The packaging includes bottles, caps and a label. Bottle tampers should not be broken prior to dispensing the IP to a patient. Osimertinib should be swallowed whole with approximately 240 mL of water, and not chewed, crushed, dissolved or divided.

Additional information about may be found in the AZD9291 Investigator's Brochure 201.

7.1.2 [¹¹C]osimertinib

The radiolabelled [¹¹C]osimertinib will be manufactured ex tempore by the PET centre Radiochemistry Laboratory at Karolinska Institutet, PPD ██████████, Solna, from a precursor "AZ13774738" supplied by PharmaSynth AS (Tartu, Estonia) and close in time to each PET examination. After synthesis, the [¹¹C]osimertinib will be dissolved in a sterile buffer solution and sterile filtered and the final product will undergo quality control prior to release for human administration. The identity of the IPs are shown in Table 6.

Table 6 Identity of investigational product

Investigational product	Dosage form and strength	Manufacturer
[¹¹ C]osimertinib ([¹¹ C]osimertinib / N-[2-[2-(dimethylamino)ethyl-methyl-amino]-4-[¹¹ C]methoxy-5-[[4-(1-methylindol-3-yl)pyrimidin-2-yl]amino]phenyl]prop-2-enamide)	Solution for intravenous injection	PET Centre, PPD ██████████
Osimertinib film-coated tablets	40 mg and 80 mg tablets	AstraZeneca Sodertalje

PET: Positron emission tomography.

Investigational product manufacturing, labelling, packaging and release will be conducted following Good Manufacturing Practice (GMP).

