3.3 Safety and tolerability variables

Safety and tolerability will be assessed by:

- Assessment of adverse events (AEs), graded by Common Terminology Criteria for Adverse Events (CTCAE) (v4.03)
- Physical examination
- Vital signs (including blood pressure [BP], pulse rate, body temperature, and weight)
- Standard 12 lead electrocardiograms (ECGs)
- Evaluation of laboratory parameters (clinical chemistry, coagulation, haematology and urine analysis)
- Echocardiogram/multiple gated acquisition scan (MUGA)
- Concomitant medications

Adverse events will be classified according to the terminology of Medical Dictionary for Regulatory Activities (MedDRA), Version 21.0 or higher (preferred term and system organ class [SOC]).

Adverse events reported before any administration of osimertinib will be listed only and be referred to as “pre-treatment”. Similarly, AEs reported before any administration of osimertinib that continue after the first administration without worsening will also be classified as “pre-treatment”.

A treatment emergent AE (TEAE) will be defined as any AE with start date and time on or after the first IV dosing of osimertinib in imaging phase up to 30 days after their last study treatment administration or immediately before initiation of any other cancer therapy, whichever occurs first.

For laboratory data, vital signs and ECG data, baseline is defined as the latest result obtained prior to the first IV dose of osimertinib in the imaging phase.

For all safety data, an on-treatment period is from after the first IV dose of osimertinib in the imaging phase, up to and including the follow-up visit.

Patients not participating in the continued access phase or who discontinue treatment during the imaging phase will return to the clinic for follow-up assessments 30 days (± 7 days) after their last administration of osimertinib in the imaging phase. If the patient’s last administration of osimertinib is in the continued access phase, the patient will be contacted 30 days after their last administration of osimertinib to follow up on any existing AEs/SAEs and monitor for new AEs/SAEs that may be related to the IP, and record any sudden deaths of unknown cause. This follow-up assessment will serve as the end-of study assessment for a patient.

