4.3.3 Safety parameters

Safety variables

All safety analyses will be performed on the safety analysis set.

Treatment Exposure

Treatment exposure data will be listed and summarised. Total exposure time and actual exposure time will be summarized using descriptive statistics for oral osimertinib exposure while frequency count of subjects taking number of doses (1, 2 or 3) will be presented for [¹¹C]osimertinib exposure.

Adverse Events

All AEs will be listed for each patient, and TEAEs will be summarised.

The following summary tables will be presented across all patients.

- Summary of number (%) of patients who had at least one AE in any category (Any AE, any causally related AE, any AE of CTCAE grade 3 or higher, any causally related AE of CTCAE grade 3 or higher, any AE with outcome = death, any causally related AE with outcome=death, any SAE (including events with outcome = death), any causally related SAE (including events with outcome = death), any SAE leading to discontinuation of investigational product (IP ie, osimertinib), any causally related SAE leading to discontinuation of IP, any AE leading to discontinuation of IP, any causally related AE leading to discontinuation of IP, any other significant AE, any other causally related significant AE (OAE)).
- Summary of number (%) of patients who had at least 1 AE by system organ class and preferred term presented by maximum reported CTCAE grade.
- Summary of number (%) of patients who had at least 1 AE with CTCAE grade 3 or higher by system organ class and preferred term.
- Summary of number (%) of patients who died and a listing of deaths.
- A listing of key information for SAEs, and a listing of key information for SAEs with outcome other than death will be presented.
- A listing of key information for AEs leading to discontinuation of IP will be presented.
- Summary of number (%) of patients who had an AE which started prior to study treatment or more than 30 days after last dose of study treatment, by system organ class and preferred term.

Clinical laboratory variables (haematology, clinical chemistry, coagulation and urine analysis)

All laboratory safety data, incorporating haematology, clinical chemistry, coagulation and urine analysis will be listed for each patient with values outside the standard reference ranges indicated in the listings.

Observed and change from baseline values will be summarised by scheduled time point.

Vital signs (pulse and BP), body temperature and weight

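### The AE causality item and the pooled TEAE tables do not separate tracer, tablet and procedure, although the safety objective names both products

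*Protocol*

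**What the plan says.** - **Objective.** Protocol 2.3 sets one safety objective covering the tracer and the tablets: [11C]osimertinib "IV doses and multiple oral doses of osimertinib in NSCLC patients with BM". SAP 1.1 repeats it.
- **Products.** Protocol 7.1.2 uses the plural, "The identity of the IPs are shown in Table 6", and that table has two rows: the IV solution and the tablets.
- **Causality, every AE.** Protocol 6.3.3 collects "Investigator causality rating against the IP (yes or no". Section 6.3.4 puts it as one question: "The Investigator will assess causal relationship between the IP and each AE".
- **Causality, serious AEs only.** Section 6.3.3 adds "Causality assessment in relation to study procedure(s" and an item on other medication; 6.3.4 says "For SAEs causal relationship will also be assessed for other medication and study procedures". Neither section extends this to non-serious events.
- **TEAE window.** SAP 3.3 defines a TEAE as "any AE with start date and time on or after the first IV dosing of osimertinib in imaging phase", running to 30 days after the last study treatment or to the start of another cancer therapy, whichever is first.
- **Tables.** SAP 4.3.3: "The following summary tables will be presented across all patients". No column separates product or period. SAP 4.1 defines a label for each product in relevant outputs, but no rule assigns an AE to a label.

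**The concern.** The two products differ in route and amount, and the tracer comes with procedures that the protocol expects to cause events of their own. Protocol 1.3.1 names pain, haematoma and possible arterial occlusion from the punctures, and temporary headache from lumbar puncture. Most such events would be non-serious, so their link to a procedure would not be recorded under 6.3.3.

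A tick for related does not say which product the investigator had in mind. In the planned tables, an event two days after PET1 in a patient who has taken no tablet sits in the same row as an event in week three of daily tablets. The report would then have exposure summaries for each product but no AE summary for the tracer without tablets, and no count of procedure-related AEs outside the serious ones.

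**Working it through.** The plan states no sample-size, power or error-rate figure on this point, so there is nothing to reproduce. The check sets the sections side by side and adds some simple arithmetic.

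**1. Length of the tracer-only interval.** PET1 is on Day 1. The first tablet is taken on the PET2 day, which Protocol 7.2 allows from Day 2 up to Day 8: 2 − 1 = 1 day to 8 − 1 = 7 days. Table 1 footnote c gives 1 to 6 days.

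**2. Share of the TEAE window.** Assume the last dose is on Day 29 with no continued access. The window is Day 1 to Day 29 + 30 = Day 59, that is 59 days. Shares: 1/59 = 1.7% to 7/59 = 11.9%. With Day 29 ± 3 (Protocol 7.2) the window is 56 to 62 days, and the extremes are 1/62 = 1.6% and 7/56 = 12.5%. Continued access lengthens the window and lowers the share.

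**3. Can these events be identified?** AE start and stop dates and times are collected (Protocol 6.3.3). Dates and times of doses are recorded (Protocol 7.5). All AEs are listed by patient (SAP 4.3.3). So they can be identified; only a planned summary is missing.

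**4. Is an event in the interval classified unambiguously?** SAP 3.3 calls an AE pre-treatment if it precedes any administration of osimertinib, and starts TEAEs at the first IV dose. Take an AE on Day 3 with the first tablet on Day 8.
- If unqualified osimertinib includes the tracer, the event is treatment-emergent only. SAP 2.1 and 4.2.1, which count the tracer as dosing, favour this reading.
- If it means the tablet, the event is both pre-treatment and treatment-emergent. The gloss in SAP 4.3.3 that equates the IP with osimertinib, without naming the tracer, leaves this open.

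SAP 4.3.3 also plans a table of AEs that began before study treatment. On the first reading it excludes these events; on the second it would mix them with screening events. Neither reading yields a tracer-only summary.

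**5. Where procedure events fall under an onset split.**

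| Source | Timing | Column |
|---|---|---|
| Screening lumbar puncture | before Day 1 | outside the TEAE window |
| PET1 arterial line | Day 1 | before first tablet, if onset follows the injection |
| PET2 arterial line | PET2 day | on or after first tablet |
| PET3 arterial line (may be omitted, Protocol 5.3.2.2) | Day 29 | on or after first tablet |
| PET3-day lumbar puncture | Day 29 | on or after first tablet |

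Most procedure events would therefore stay in the tablet column. Isolating them needs a procedure rating on every AE.

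**6. What a tracer-only column could show.** With 0 events in n patients, the one-sided 95% upper limit is 1 − 0.05^(1/n): 22.1% for n = 12 and 31.2% for n = 8. The chance of at least one event in 12 patients is 1 − (1 − p)^12: 46% for an assumed p of 5% and 72% for an assumed p of 10%.

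**The case against.** Several points on the other side stand.

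- A reader might infer that the safety objective cannot be answered separately for the tracer. The documents do not support that: step 3 shows that events before the first tablet can be recovered, and with about 12 patients they can be read from the listings.
- The objective is worded jointly and does not ask for product-specific conclusions. Splitting it is a reasonable reading, not a stated requirement. Exposure is already summarised by product, and laboratory, vital-sign and ECG data are shown by scheduled time point.
- A reader might want separate causality boxes for tracer and tablet. After the first tablet these would add little. The same substance is given at no more than 10 µg against 80 mg, a ratio of at least 80,000/10 = 8,000, and the tracer follows the tablet by about 6 hours at PET2 and PET3. That limit comes from the design.
- A reader might try to say by how much procedure events inflate the overall AE row. The documents give no procedure event rate. Each patient counts once in that row, so a procedure event changes it only if that patient has no other TEAE. The preferred-term tables would show a haematoma or headache by name.
- The case report form is not among the documents and may hold more fields than Protocol 6.3.3 lists.

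What remains is that the specified tables do not show the recoverable information, and that the specified variables omit procedure causality for non-serious AEs. An onset date cannot replace that rating.

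**Conclusion.** The point holds as a gap in planned collection and presentation, not as an inability to assess the tracer. The specified causality item and TEAE tables do not separate tracer, tablet and procedure, and no planned AE summary isolates the 1 to 7 days (1 to 6 by footnote c) between PET1 and the first tablet. On the assumptions in step 2 that is about 2% to 12% of the TEAE window. The SAP wording also leaves open a double classification of events in that interval.

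The benefit is modest. A tracer-only column describes; with an upper limit of about 22% after zero events in 12 patients, it cannot establish tracer safety. Tracer-versus-tablet attribution at PET2 and PET3 stays limited whatever form is used. The primary imaging endpoint is not affected. The change is still worth making, because the objective names both products and the split uses data already collected.

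**What to change.** 1. **SAP 4.3.3:** present the TEAE overview and the system organ class and preferred term tables in three columns: onset from the first [11C]osimertinib injection to before the first tablet; onset on or after the first tablet; total. This needs no new data.
2. **SAP 3.3, carried through to 4.3.3:** state whether unqualified osimertinib, in the pre-treatment definition and in the gloss on the IP, includes the tracer, so that an event between PET1 and the first tablet has one classification only. This is a wording change.
3. **Protocol 6.3.3 and 6.3.4, and the case report form:** extend the study-procedure causality rating from SAEs to all AEs, and tabulate procedure-related AEs separately in the SAP. This adds one field to the AE page. For patients already enrolled it can be completed only by query, and ratings made in hindsight are weaker than those made at the time.

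The text introducing these tables should say that the tracer-only column is descriptive and that the on-or-after-first-tablet column still contains events from the PET2 and PET3 procedures.

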6.3.4 Causality collection

The Investigator will assess causal relationship between the IP and each AE, and answer 'yes' or 'no' to the question 'Do you consider that there is a reasonable possibility that the event may have been caused by the IP?'

For SAEs causal relationship will also be assessed for other medication and study procedures. Note that for SAEs that could be associated with any study procedure the causal relationship is implied as 'yes'.

A guide to the interpretation of the causality question is found in Appendix A to the CSP.

6.3.5 Adverse events based on signs and symptoms

All AEs spontaneously reported by the patient or care provider or reported in response to the open question from the study centre staff: "*Have you/the child had any health problems since the previous visit/you were last asked?*" or revealed by observation will be collected and recorded in the pCRF. When collecting AEs, the recording of diagnoses is preferred (when possible) to recording a list of signs and symptoms. However, if a diagnosis is known and there are other signs or symptoms that are not generally part of the diagnosis, the diagnosis and each sign or symptom will be recorded separately.

6.3.6 Adverse events based on examinations and tests

The results from protocol laboratory tests, vital signs, ECGs and other safety assessments will be summarised. Deterioration as compared to baseline in protocol-mandated parameters should therefore only be reported as AEs if they fulfil any of the SAE criteria or are the reason for discontinuation of treatment with the IP, unless clearly due to progression of disease under study.

If deterioration in a laboratory value/vital sign is associated with clinical signs and symptoms, the sign or symptom will be reported as an AE and the associated laboratory result/vital sign will be considered as additional information. Wherever possible the reporting Investigator uses the clinical, rather than the laboratory term (eg, anaemia versus low haemoglobin value). In the absence of clinical signs or symptoms, clinically relevant deteriorations in nonmandated parameters should be reported as AE(s).

Deterioration of a laboratory value, which is unequivocally due to disease progression, should not be reported as an AE/SAE.

Any new or aggravated clinically relevant abnormal medical finding at a physical examination as compared with the baseline assessment will be reported as an AE.

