5.2.3 ECG

Twelve-lead ECGs will be obtained after the patient has been resting semi-supine for at least 10 minutes. All ECGs should be recorded with the patient in the same physical position. For each time point 3 ECG recordings should be taken at about 5 minute intervals. A standardised ECG machine should be used and the patient should be examined using the same machine throughout the study if possible.

After paper ECGs have been recorded, the Investigator or designated physician will review each of the ECGs and may refer to a local cardiologist if appropriate. A paper copy should be filed in the patient’s medical records. If an abnormal ECG finding at screening or baseline is considered to be clinically significant by the Investigator, it should be reported as a concurrent condition. For all ECGs details of rhythm, ECG intervals and an overall evaluation will be recorded.

ECG data will be collected digitally and will be transferred electronically for central analysis as described in the study specific ECG manual. The investigator may choose to perform a non-digital ECG at the time of the screening visit in order to identify patients eligible for study entry. If a non-digital ECG is performed at the screening visit it cannot subsequently be used as a baseline recording, in this situation an ECG will need to be collected on the baseline visit in digital form.

Heart rate, PR, R-R, QRS and QT intervals will be determined and reviewed by an external cardiologist.

If there is a clinically significant abnormal ECG finding during the treatment period, this should be recorded on the AE pCRF, according to standard AE collection and reporting processes (see Section 6.3.6). A 28-day follow-up assessment will be required if an on-treatment assessment was abnormal at the time of discontinuation of the IP or study, to confirm reversibility of the abnormality. Information on osimertinib dose reduction for QTc interval prolongation is detailed in Section 6.8.4.

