6.8 Management of IP related toxicities

Patients who have IP-related toxicities requiring dose interruption or dose reduction may be discontinued from the imaging phase and entered into the CAP following discussion with an AstraZeneca representative. Dose reduction is not allowed in the imaging phase of the study; if the Investigator feels that they need to reduce the IP dose due to toxicity, then the patient should be discontinued from the imaging phase and may be entered into the CAP.

The following text is guidance for Investigators who treat patients with osimertinib in continued access:

If a patient experiences a CTCAE grade 3 or higher and/or unacceptable toxicity (any grade), including a dose-limiting toxicity not attributable to the disease or disease-related processes under investigation, dosing will be interrupted and supportive therapy administered as required in accordance with local practice/guidelines.

If dose reduction is necessary, then the dose of osimertinib should be reduced to 40 mg taken once daily. Patients who reduce to the 40 mg dose must remain on the 40 mg dose for the remainder of the study.

Dose interruption and reduction guidelines are provided in Table 4.

Table 4 Osimertinib dose adjustment information for adverse reactions

Target Organ	Adverse Reaction	Dose Modification
Pulmonary	ILD/Pneumonitis	Permanently discontinue osimertinib
Cardiac	QTc interval greater than 500 msec on at least 2 separate ECGs	Withhold osimertinib until QTc interval is less than 481 msec or recovery to baseline if baseline QTc is greater than 481 msec within 3 weeks of onset, then restart at a reduced dose (40 mg) or at 80mg (at the discretion of the investigator).
	QTc interval prolongation with signs/symptoms of serious arrhythmia	Permanently discontinue osimertinib
Other	Grade 3 or higher adverse reaction If grade 3 or higher adverse reaction improves to grade 0-2 after withholding of osimertinib for up to 3 weeks Grade 3 or higher adverse reaction that does not improve to grade 0-2 after withholding for up to 3 weeks	Withhold osimertinib for up to 3 weeks Osimertinib may be restarted at the same dose (80 mg) or a lower dose (40 mg) Permanently discontinue osimertinib

ECG: Electrocardiogram; ILD: Interstitial lung disease; msec: Millisecond; QTc:QT interval corrected.

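### Protocol 6.3.6 keeps an asymptomatic, non-serious imaging-phase finding that only interrupts osimertinib out of the AE data; for ECGs this contradicts 5.2.3, and for laboratory values the SAP plans no graded table

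*Protocol*

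**What the plan says.** **Mandated tests.** Protocol 6.3.6 notes that results of the protocol laboratory tests, vital signs, ECGs and other safety assessments will be summarised, and draws a reporting rule from that: "Deterioration as compared to baseline in protocol-mandated parameters should therefore only be reported as AEs if they fulfil any of the SAE criteria". The rule has one alternative trigger, which concerns stopping treatment: "or are the reason for discontinuation of treatment with the IP, unless clearly due to progression of disease under study". A further sentence covers symptomatic cases: "If deterioration in a laboratory value/vital sign is associated with clinical signs and symptoms, the sign or symptom will be reported as an AE". For parameters the protocol does not mandate, a clinically relevant deterioration without symptoms is reported as an AE.

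**ECGs.** Protocol 5.2.3 sets a different trigger: "If there is a clinically significant abnormal ECG finding during the treatment period, this should be recorded on the AE pCRF". The same sentence then refers to 6.3.6 for the reporting process.

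**Interruption in the imaging phase.** Protocol 6.8 says: "Patients who have IP-related toxicities requiring dose interruption or dose reduction may be discontinued from the imaging phase" and entered into the continued access phase (CAP). Dose reduction is not allowed in the imaging phase. Protocol 7.5 has dates of missed or held doses recorded. The actual exposure formula in SAP 3.3 subtracts imaging-phase interruption days.

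**What an AE record carries.** Protocol 6.3.3 lists CTCAE grade, the causality rating and "Action taken with regard to IP" among the variables collected for each AE.

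**What the SAP tabulates.** In SAP 4.3.3 the AE overview has rows for grade 3 or higher, causally related events and discontinuation of IP, and none for interruption. Laboratory data are listed with out-of-range flags, and "Observed and change from baseline values will be summarised by scheduled time point". For QTcF there is a separate outlier table.

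**The concern.** The safety objective is assessed through CTCAE-graded AEs together with ECGs, vital signs and laboratory parameters. A laboratory or ECG change that makes the Investigator hold the drug is one that a reader of the safety section will look for. If it causes no symptoms, meets no SAE criterion and does not end treatment, 6.3.6 keeps it out of the AE data. It then reaches neither the grade 3 or higher row nor the causally related row. The Investigator's view of causality is not captured anywhere else.

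For ECG findings there is a second problem. Two sections give different instructions for the same event, and the cross-reference from 5.2.3 to 6.3.6 does not say which governs. Whether a clinically significant but non-serious ECG finding becomes an AE would depend on which section the site reads.

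**Working it through.** The plan states no figure on this point, so the check is mainly a comparison of the rules.

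1. **Apply 6.3.6 to a test case.** Take an asymptomatic, non-serious deterioration in a mandated laboratory value in the imaging phase. Osimertinib is held and then resumed.
   - SAE criterion met? No, by assumption.
   - Reason for discontinuing the IP? No, treatment resumes.
   - Accompanying sign or symptom? None.
   - Result: not an AE.

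2. **Vary the case.** The patient instead leaves the imaging phase under 6.8 and enters the CAP while staying on osimertinib. The IP has not been discontinued, so 6.3.6 gives the same result. The finding ended the patient's imaging phase without becoming an AE.

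3. **Repeat with an ECG finding.** Suppose the finding is clinically significant, asymptomatic and non-serious, and the drug is only paused.
   - Protocol 5.2.3: record on the AE form.
   - Protocol 6.3.6, which names ECGs among the assessments it covers: do not report as an AE.
   - The two rules give opposite answers. The conflict is confined to ECGs, because 5.2.3 does not deal with laboratory values or vital signs.

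4. **See what the SAP recovers outside the AE tables.**
   - *QTcF:* patients above 450, 480 and 500 ms, and with increases above 30, 60 and 90 ms, are counted at any assessment after the first microdose. The 500 ms category matches the value that protocol 6.8.4 associates with interruption. The extreme value is recovered; causality and action on the IP are not.
   - *Laboratory values:* SAP 4.1 includes minimum and maximum in the by-visit statistics, so an extreme can appear there. SAP 4.2.2, however, uses the value closest to the planned day in each window, so an unscheduled extreme can drop out. That section also has a rule for on-treatment maxima and minima that includes unscheduled values, but 4.3.3 names no laboratory table to which it would apply. No table by CTCAE grade, shift or worst value is planned.
   - *Interruptions:* total and actual exposure show that days were lost, but not why. No output counts findings that led to interruption.

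5. **Size.** With the planned number of about 12 patients, one unrecorded event changes an incidence by 1/12 = 8.3 percentage points. For illustration, a true 2/12 (16.7%) would be reported as 1/12 (8.3%), and a true 1/12 as 0/12. The documents do not say how many such events to expect, and the number may be zero.

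**The case against.** The restriction in 6.3.6 is deliberate. Mandated results are to be summarised in their own tables, so reporting them again as AEs would be duplication; non-mandated results have no planned summary and need the AE route. A reader might infer from the contrast that the section is back to front. Its stated reason does not support that. What can be said is that the promised summary is thin for laboratory data.

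A reader might also infer that any toxicity that pauses osimertinib escapes the AE data. It does not. Accompanying signs and symptoms are AEs under 6.3.6. Medically important events count as serious under 6.2, and Appendix A gives neutropenia or anaemia requiring transfusion as an example. Potential Hy's Law cases have their own process in 6.3.7 and Appendix D. Only asymptomatic findings that meet no SAE criterion fall through.

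Nor is it right that no other SAP output would show such a finding. The QTcF table counts the extremes, there is an ECG shift table, laboratory minima and maxima appear by visit, and every laboratory value is listed with a flag. With about 12 patients, a reader could match listed values to held-dose dates and derive a laboratory grade. This stands. What cannot be rebuilt is the causality rating and the Investigator's recorded action; what is not tabulated is the grade.

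Finally, the detailed interruption guidance in 6.8 is introduced as applying to continued access, where non-serious AEs are not collected (protocol 4.3). Amending 6.3.6 recovers nothing there. The point concerns the imaging phase, with its oral treatment of at least 21 days.

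**Conclusion.** The point holds as a narrow reporting gap plus one contradiction. Under 6.3.6, an asymptomatic, non-serious imaging-phase deterioration in a mandated parameter is not an AE if it only interrupts osimertinib or moves the patient to continued access on drug. For ECG findings, 5.2.3 and 6.3.6 contradict each other and must be reconciled. For laboratory values, the reason given in 6.3.6 for limiting AE reports is only partly met by the SAP.

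The tables of grade 3 or higher and causally related AEs could therefore read low. The documents do not support saying that they will, or by how much: 8.3 points per event is arithmetic on the planned 12 patients, not an estimate of bias. The conclusion assumes that sites apply 6.3.6 as written and that at least one such event occurs. The study is descriptive, so no formal inference is affected. This is a worthwhile, inexpensive improvement.

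**What to change.** - **Protocol 6.3.6:** add that deterioration in a mandated parameter is also reported as an AE when it leads to interruption of the IP or when the Investigator judges it clinically significant. The second condition brings 6.3.6 into line with 5.2.3, so the cross-reference no longer points to a narrower rule. It also allows a finding that moves a patient to continued access to be captured.
- **SAP 4.3.3:** add a table of baseline grade against worst on-treatment CTCAE v4.03 grade, including unscheduled values, for the gradable laboratory variables in protocol Table 2.

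The cost is one protocol sentence and one table from data already collected. The downside is a few more non-serious AE records and slightly higher reported AE rates. No dosing rule changes.
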